3.2.2 Exclusion criteria

- Pregnancy.
- Starting or switching from fampridine (Fampyra®) in the last 4 weeks.
- Height and weight outside the secure standard of safe use, described in the safety guides.
- Contraindications for Atalante training (eg, bone instability, history of osteoporosis or osteoporotic fractures).
- Subjects under Corticosteroids treatment or relapse.
- Changes in disease-modifying and symptomatic therapy for MS during the study period.
- Subjects with psychiatric or cognitive comorbidities that may interfere with the trial.
- Whose joint centers cannot be aligned Atalante's.
- Ranges of motion below:
 - Knee: 5° extension, 110° flexion

- Ankle: 0° dorsiflexion, 9° plantar flexion, 18° inversion and eversion
- Hip: 115° flexion, 15° extension, 17° abduction, 10° adduction, 10° medial rotation, 20° lateral rotation
- Severe spasticity (greater than Ashworth 3) or uncontrolled clonus.
- Severe concurrent medical diseases: infections, circulatory, heart or lung, pressure sores.
- Active implantable medical device.

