Gait and balance disturbances in MS are already common even in the early stages of the disease. Half of the patients refer some alteration in the quality of their gait within the first month after diagnosis, reaching 90% at 10 years of evolution.⁴ ⁵ Furthermore, gait is the most valuable body function for MS patients, both for those with less than 5 years of evolution and for those with more than 15 years, as walking restriction hardly affects their activity and participation level.⁷

Gait disturbance is caused by multiple factors such as decreased muscle strength, balance, coordination, and proprioception, impaired vision, spasticity, fatigue and even cognitive impairment.⁴

Some impairments arise in the physical and social context of each patient, limiting participation in activities or therapies to improve balance, fatigue, strength and gait characteristics such as fatigue, high risk of falls or high disability.⁷

This would support the development and application of rehabilitation strategies for mitigating the energetic penalties of gait abnormalities during ambulation. Some of these interventions include aerobic, resistance, yoga, and combined exercise training, that have shown significant improvements in walking endurance regardless of outcome measures (6MWT, 2MWT).⁸

New emerging approaches might involve Robot-assisted gait training. In the last 5 years a lot of robotic solutions that offer both strategies of support in daily living and rehabilitative devices have appeared. Some studies have shown that people with multiple sclerosis and severe gait impairment who participated in Robot-assisted gait training (RAGT) achieved significant improvement in lower limb muscle strength and increased their walking speed, although the effect was not long-lasting.⁹

In the last years evidence about robot-based rehabilitation for PwMS has been published, and currently, more than 5 devices have been approved for its use in gait neurorehabilitation. Yeh et al. concluded that Robotic locomotor training limitedly affects motor functions of multiple sclerosis, but improves fatigue and spasticity, it is safe and well-tolerated for PwMS and less demanding for physical therapists.¹⁰ Bowman et al. concluded that Robotic-Assisted Gait therapy (RAGT) improves balance and gait out-

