3.2.1 Inclusion criteria

- Male or female, between 18 and 75 years of age.
- Confirmed diagnosis of MS.
- EDSS from 6.0 to 7.0.
- Able to maintain the upright position on a daily basis.
- Stable course of disease-modifying therapy over the past 6 months.
- Clinical comorbidity asymptomatic (i.e., no underlying cardiovascular disease)
- Height: between approximately 1.50 m. and 1.90 m.
- Willingness to visit the Multiple Sclerosis Center of Catalonia (Cemcat) for testing and training.
- Gait disorder conditioned by paresis or hemiparesis associated with ataxia or sensory problems.
- Patient having given written consent.
Atalante is able to accommodate the following limb lengths:
- Thigh: 380-460mm.
- Distance between the ground and the joint space of the knee (to be measured while wearing the shoes they intend to wear with Atalante):
 - 457–607mm for patient with an ankle dorsiflexion $\geq 16^\circ$
 - 457–577mm for patient with an ankle dorsiflexion between 13° et 16°
 - 457–567mm for patient with an ankle dorsiflexion between 10° et 13°
 - 457–557mm for patient with an ankle dorsiflexion between 0° and 10°
- Hip with less or equal to 460mm when seated.
- Maximum weight: 90 kg.

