3.3 Enrollment and Screening

Subjects will be evaluated for their eligibility from neurorehabilitation and neurology outpatient clinics at the Multiple Sclerosis Center of Catalonia (Cemcat).

Potential subjects will be referred to the study via Cemcat Physicians. A member of the research team will screen the referral and confirm they meet the necessary inclusion and exclusion criteria. Following confirmation of criteria, potential subjects will be contacted by phone to schedule an initial visit for consent and baseline assessment.

Additionally, peripheral blood (6ml) will also be taken from all subjects at baseline (T1).

Prior to all testing, each of the 60 selected participants will have time to read the consent form and ask questions (see Draft Informed Consent). The consent process will take place at the Multiple Sclerosis Centre of Catalonia (Cemcat, Vall d'Hebron Barcelona Hospital Campus, [name]).

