Differentially open ATAC-seq peaks will then be annotated with regard to functional and positional information. HOMER will be used to annotate peaks based on the relative gene position (promoter (± 2 kb of known TSS), intergenic,

intronic, among others). For functional annotation of peaks, we will use a simplified version of the 18-state ChromHMM-derived chromatin states (such as TSSs, enhancers, repressed polycomb, transcriptionally active, or other states such as ZNFs or heterochromatin) obtained from Roadmap Epigenomics data for PBMC and T cell subsets.

For gene-based analyses, HOMER will be used to assign each differentially open ATAC-seq peak to the nearest TSS, as measured from the peak center. We will then assess enrichment using the hypergeometric test followed by Benjamini-Hochberg FDR adjustment for P values, as previously mentioned.

Further functional and ontological enrichment analyses will be performed using ClueGO and WikiPathways that will allow us to identify pathways among genes associated to differentially open peaks.

Finally, we will scan the data for transcription factor (TF) footprints using the PIQ algorithm which integrates genome-wide TF motifs with chromatin accessibility estimates profiled at base pair resolution to generate a list of possible footprint matches for a motif. In a nutshell, this will allow the identification of chromatin accessibility blueprint generated by the different rehabilitation therapies tested in this trial, as well as gather valuable data of its underlying molecular mechanisms that in turn might lead to the identification of novel therapeutic targets.

Type outcome	Test	Baseline (T1)			RAG Session 1-24 (S1-S24)			end of training (T2)			Follow up at 2 months (T3)			Follow up at 1 year (T4)		
		CRO	PROMs	Blood sample	CRO	PROMs	Blood sample	CRO	PROMs	Blood sample	CRO	PROMs	Blood sample	CRO	PROMs	Blood sample
Pain	1	Pain registry		x			x			x			x			
Physiologic indicators	2	Heart rate	x			x			x			x				
	3	Arterial pressure	x			x			x			x				
Effort	4	Rating perception exertion The Borg R.P.E scale				x										
Fatigue:	5	Modified fatigue scale (MFIS)		x						x						
Depression	6	Hospital Anxiety and Depression Scale (HADS)		x						x						
Health-related quality of life	7	MSQoL 54 Health Survey		x						x						
Mobility	8	Modified Rivermead Mobility Index	x						x			x				
Disability	9	Expanded Disability Status Scale (EDSS) de Kurtzke	x						x			x				

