3.4.2 Schedule

Following completion of day 1 assessments and randomization, all subjects will be scheduled for the intervention phase of the study. Each participant will receive 24 sessions of RAGT or cRHB scheduled for three times a week for 8 weeks. If a subject cancels a treatment session, it will be counted as missed session. If a subject misses three consecutive treatment sessions, they will be dropped from the study due to inconsistency in treatment carryover. Cancellations and changes in patient scheduling represent a true clinical environment and represents normal clinical patient management.

At the end of the intervention phase, a new exploration will be carried out.

[figure not shown]

Figure 1 schedule

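### An exclusion criterion on therapy changes can be met almost only after randomisation, and the plan neither says what then happens nor protects the randomised comparison

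*Combined protocol and SAP*

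**What the plan says.** Section 3.2.2 includes this item among the exclusion criteria: "Changes in disease-modifying and symptomatic therapy for MS during the study period". Two other criteria on MS drugs look backward from entry: "Stable course of disease-modifying therapy over the past 6 months" (3.2.1) and "Starting or switching from fampridine (Fampyra®) in the last 4 weeks" (3.2.2).

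On timing, section 3.3 states "A member of the research team will screen the referral and confirm they meet the necessary inclusion and exclusion criteria", and then "Following confirmation of criteria, potential subjects will be contacted by phone to schedule an initial visit for consent and baseline assessment". Section 3.4.2 places allocation after that: "Following completion of day 1 assessments and randomization, all subjects will be scheduled for the intervention phase of the study".

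The study period is not defined. Table 1 runs from baseline (T1) through the end of training (T2) and two months (T3) to one year (T4).

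No section says what is done with a randomised participant whose therapy changes. Section 4 names no analysis set, no intention-to-treat principle, no missing-data method and no rule for therapy changes. The one explicit rule for an event after randomisation, three missed sessions in a row, takes the participant out of the study (3.4.2).

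**The concern.** An eligibility criterion should be decidable before allocation. This one depends on events that mostly lie after it, so a site can follow it only by declaring a randomised person ineligible.

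That matters if the trigger is related to outcome and acts unequally in the two arms. Both are plausible. The background reports that robotic training has limited effect on motor function "but improves fatigue and spasticity, it is safe and well-tolerated for PwMS". Spasticity and fatigue are targets of symptomatic treatment, and the trial measures both. Only the rater is blinded (3.1). Section 3.4 also has the therapist rate spasticity before each robot session and register robot-related pain after it, with no matching per-session check described for the control arm. Symptoms that might prompt a change are therefore watched more closely in one arm.

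At stake is the comparison of 10-metre walking speed between 30 and 30 participants, and the secondary comparisons with it. If removal is not intended, the silence still leaves sites and analysts free to treat the same event differently after outcomes are known.

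**Working it through.** **Timing.** The documented order is: criteria confirmed at referral; telephone contact; consent and baseline visit; randomisation with the day 1 assessments; eight weeks of training; follow-up. A change during the study cannot be known at the first step. The only pre-allocation window in which it could occur is between referral and day 1, and only if the study period is taken to start at referral. Hence almost only after randomisation, rather than strictly only.

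**How many people.** The plan gives no figure on this point to reproduce, so the rate is an assumption.

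- Inputs from the documents: 60 participants, 30 per arm (3.1); T2 at 8 weeks; T3 read as two months after T2.
- Assumed: r = 0.2 to 0.4 therapy changes per person-year, at a constant rate.
- Formula: share affected by time t = 1 − exp(−r·t); number = 60 × share.

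| Time | t (years) | Share, r = 0.2 | Share, r = 0.4 | Number of 60 |
|---|---|---|---|---|
| T2 | 8/52 = 0.154 | 3.0% | 6.0% | 1.8 to 3.6, about 2 to 4 |
| T3 | 8/52 + 2/12 = 0.32 | 6.2% | 12.0% | 3.7 to 7.2, about 4 to 7 |

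**Effect on the responder proportion at T2.** Section 2.1 treats a 20% gain in speed as clinically relevant, so take responders on that definition. Assume no true difference: 12/30 = 40% in each arm.

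- All 2 to 4 removed are non-responders in one arm: 12/28 = 42.9% to 12/26 = 46.2%. Apparent difference 2.9 to 6.2 points, the ceiling for this mechanism.
- Unequal but mixed, 1 non-responder removed in one arm and 2 in the other: 12/29 = 41.4% against 12/28 = 42.9%, about 1.5 points.
- Balanced, 2 non-responders removed in each arm: 12/28 in both. No difference, though both proportions are inflated.
- Opposite mechanism, all 2 to 4 removed are responders in one arm (drugs reduced because symptoms improved): 10/28 = 35.7% to 8/26 = 30.8%, that is 4.3 to 9.2 points the other way.

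The last line shows why the direction cannot be stated in advance.

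**The case against.** The strongest reply is that the protocol never orders removal. Where it means removal, as with missed sessions, it says so. Since eligibility is checked once, before consent, the line may have been meant as no change planned at entry. This stands in part: removal is the literal effect of an exclusion criterion, not a stated procedure, and the actual handling is unspecified. But the entry-only reading is not what is written, and the authors used explicit look-back windows elsewhere when they meant them.

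Four stronger readings are tempting, and the documents do not support them.

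- **That exclusions are known to follow treatment response.** The background says nothing about drug changes. The link is inference, and reductions among improvers and escalations among non-improvers would push in opposite directions.
- **That the line is redundant before entry.** The six-month rule covers disease-modifying drugs only. Apart from fampridine, and the corticosteroid and relapse exclusion, no pre-entry stability rule covers symptomatic treatment.
- **That the one-year count is the relevant one.** The same rates give 1 − exp(−0.2) = 18% to 1 − exp(−0.4) = 33% by one year, about 11 to 20 people. But the 10-metre walk appears in Table 1 at three visits, which read as T1, T2 and T3; what is described at or after the one-year stage is a blood sample if possible.
- **That data already collected at T2 would be deleted after a later change.** Nothing calls for this, although nothing rules it out.

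It is also fair to say that larger distortions need larger removal rates. Type I error of about 5.4% to 7.9% arises if 10% to 20% of non-responders are removed in one arm and 20% to 40% in the other. With 18 non-responders per arm, even the mildest case removes 1.8 + 3.6 = 5.4 people, more than the 2 to 4 expected by T2.

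**Conclusion.** The point holds as a flaw in a stated rule. The criterion can be met almost only after allocation, its literal effect is removal, and section 4 contains nothing that keeps such participants in the comparison.

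On the assumed rates, 2 to 4 of 60 would be affected by T2 and 4 to 7 by T3. If every removal by T2 were a non-responder in the same arm, the spurious difference would be at most about 3 to 6 points; it is near zero if removals are balanced, and reversed in sign if responders are the ones removed. These figures rest on an assumed rate, an assumed 40% response in both arms and the assumption that removal is actually carried out. They show scale and are not an estimate of bias. The documents do not show that the trial will be biased, only that the rule permits it.

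**What to change.** - Reword the criterion so that it is decided before randomisation, for example that no change in these therapies is planned at entry, and delete the reference to the study period. Whether to add a look-back window for symptomatic treatment, and how long, is for the investigators.
- State that a therapy change after randomisation is recorded by drug class, date and arm, and is not a reason for exclusion from follow-up or analysis.
- State in section 4 that all randomised participants stay in the primary 10-metre walk comparison in their assigned arm.
- Specify one sensitivity analysis, for example the primary comparison repeated with participants whose therapy changed before T2 counted as non-responders on the 20% threshold.

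The cost is one reworded line, a short paragraph in section 4 and one extra field in data capture. The downside is that some outcomes will be measured under changed co-medication. The estimate is then a treatment-policy effect, the effect of assignment including any later drug changes, and the plan should say so. None of this alters clinical care.

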3.3 Enrollment and Screening

Subjects will be evaluated for their eligibility from neurorehabilitation and neurology outpatient clinics at the Multiple Sclerosis Center of Catalonia (Cemcat).

Potential subjects will be referred to the study via Cemcat Physicians. A member of the research team will screen the referral and confirm they meet the necessary inclusion and exclusion criteria. Following confirmation of criteria, potential subjects will be contacted by phone to schedule an initial visit for consent and baseline assessment.

Additionally, peripheral blood (6ml) will also be taken from all subjects at baseline (T1).

Prior to all testing, each of the 60 selected participants will have time to read the consent form and ask questions (see Draft Informed Consent). The consent process will take place at the Multiple Sclerosis Centre of Catalonia (Cemcat, Vall d'Hebron Barcelona Hospital Campus, [name]).

3.4 Assessments

The following information will be collected for all patients: age, sex, weight, height, type of MS, years from the diagnosis, Expanded Disability Status Scale (EDSS) and type of support device.

To ensure that training sessions are well tolerated, we will assess patients' blood pressure and heart rate weekly. We will also monitor the appearance of pain in any part of the body related to the RAGT at end of each training session using a pain registry (type of pain, location, intensity)²⁷.

3.4.1.1 To reduce the incidence of any type of muscle injury the physical therapist before each RAGT session will assess the level of spasticity using the Numeric Rating Scale measure of spasticity (NRS). The 0–10 NRS asks patients to indicate their level of spasticity on a scale of 0–10, where 0 is no spasticity and 10 is the worst possible spasticity. This type of rating tool is widely utilized in clinical settings to quickly assess pain.²⁸

A record of any unexpected Serious Adverse Events (SAE) within trial episodes will be kept. These are defined as death, a life-threatening adverse event or an event occurring as a result of the use of the device that requires medical intervention.

After the 8 weeks of rehabilitation treatment (T2) and, if possible, one year after T4, peripheral blood (6ml) will be taken from all subjects to perform the subsequent molecular analysis.

Molecular analysis

Peripheral blood mononuclear cells (PBMCs) will be purified using the Ficoll-Hypaque density gradient method according to manufacturer's instructions. Briefly, whole blood will be extracted by venepuncture and collected in CPT Vacutainer tubes (Becton Dickinson, BDAM362781) and centrifuged at 2250g for 25 min. Supernatant will then be collected, and washed twice with enriched saline (0.9% NaCl, 2%FBS). PMBC containing pellet will then be resuspended with 1 ml of complete media (RPMI1640 + 2% FBS) and cells will be counted and assessed for viability using a Countess 3 automated cell counter (Invitrogen). PBMCs will be adjusted to 5×10^6 cells/ml in freezing media media (90% FBS, 10% DMSO), and frozen at -80°C using a [name]™ Freezing Container (Thermo Scientific™) for 24 h and stored in liquid nitrogen vapor phase.

Once all samples are collected, chromatin will be extracted from the frozen PBMCs. Briefly, each vial containing 5×10^6 cells will be thawed and centrifuged at 300g for 5 min at 4°C . The supernatant will then be removed, and cells will be mixed with 100 μL of lysis buffer (10 mM NaCl, 3 mM MgCl₂, 10 mM Tris-HCl pH7.4, 0.1% Tween-20, 0.1% NP40) and lysed on ice for 4 min. Followed by 2x1ml washes (10 mM NaCl, 3 mM MgCl₂, 10 mM Tris-HCl pH7.4, 0.1% Tween20) before centrifuging at 500g for 5 min at 4°C .

Next, ATAC-seq libraries will be generated according to manufacturer guidelines. Briefly, transposition mix (Illumina, Cat# 20031198) will be added to the nuclear pellets, incubated at 37°C for 30 min, and DNA purified using the QIAGEN MinElute PCR Purification Kit (QIAGEN, Cat#28004). DNA fragments will be amplified by PCR for 10 to 11 cycles and resulting libraries purified using the QIAGEN MinElute PCR Purification Kit. The libraries will then be sequenced with an Illumina Novaseq 6000 S4 flow cell using 150 bp paired-end reads (Illumina, Cat# 20027466). FASTQ files will be generated from the NovaSeq BCL outputs and used as input to the ENCODE ATAC-seq pipeline (<https://github.com/ENCODE-DCC/atac-seq-pipeline>) using the MACS2 peak-caller with all default parameters. Differential accessibility will be initially calculated between groups using the csaw package.

To identify differentially open chromatin regions between groups from ATAC-seq, the R package edgeR will be used to fit a generalized linear model (GLM) to test for the effect of rehabilitation between T0 and T1 samples. In addition to time group (T0 vs. T1), we will also compare the two different rehabilitation treatments (cRHB vs. RAGT at T1). We will also use surrogate variable analysis (SVA) to capture unknown sources of variation (e.g., batch effects, age, sex, library preparation, etc) statistically independent from time or treatment group assignments. SVA decomposes the variation that is not accounted for by known factors such as time group or treatment into orthogonal vectors that can then be used as additional covariates when fitting a model to test for differential accessibility or expression.

Benjamini-Hochberg P value correction will be used to select differentially open peaks at an FDR of 5%.

Differentially open ATAC-seq peaks will then be annotated with regard to functional and positional information. HOMER will be used to annotate peaks based on the relative gene position (promoter (± 2 kb of known TSS), intergenic,

intronic, among others). For functional annotation of peaks, we will use a simplified version of the 18-state ChromHMM-derived chromatin states (such as TSSs, enhancers, repressed polycomb, transcriptionally active, or other states such as ZNFs or heterochromatin) obtained from Roadmap Epigenomics data for PBMC and T cell subsets.

For gene-based analyses, HOMER will be used to assign each differentially open ATAC-seq peak to the nearest TSS, as measured from the peak center. We will then assess enrichment using the hypergeometric test followed by Benjamini-Hochberg FDR adjustment for P values, as previously mentioned.

Further functional and ontological enrichment analyses will be performed using ClueGO and WikiPathways that will allow us to identify pathways among genes associated to differentially open peaks.

Finally, we will scan the data for transcription factor (TF) footprints using the PIQ algorithm which integrates genome-wide TF motifs with chromatin accessibility estimates profiled at base pair resolution to generate a list of possible footprint matches for a motif. In a nutshell, this will allow the identification of chromatin accessibility blueprint generated by the different rehabilitation therapies tested in this trial, as well as gather valuable data of its underlying molecular mechanisms that in turn might lead to the identification of novel therapeutic targets.

Type outcome	Test	Baseline (T1)			RAG Session 1-24 (S1-S24)			end of training (T2)			Follow up at 2 months (T3)			Follow up at 1 year (T4)		
		CRO	PROMs	Blood sample	CRO	PROMs	Blood sample	CRO	PROMs	Blood sample	CRO	PROMs	Blood sample	CRO	PROMs	Blood sample
Pain	1	Pain registry		x			x			x			x			
Physiologic indicators	2	Heart rate	x			x			x			x				
	3	Arterial pressure	x			x			x			x				
Effort	4	Rating perception exertion The Borg R.P.E scale				x										
Fatigue:	5	Modified fatigue scale (MFIS)		x						x						
Depression	6	Hospital Anxiety and Depression Scale (HADS)		x						x						
Health-related quality of life	7	MSQoL 54 Health Survey		x						x						
Mobility	8	Modified Rivermead Mobility Index	x						x			x				
Disability	9	Expanded Disability Status Scale (EDSS) de Kurtzke	x						x			x				
Balance	10	Berg scale test and Timed Up and Go test	x						x			x				
Gait	11	Timed 10-meters walk test	x						x			x				
	12	self-report 12-Item Multiple Sclerosis Walking Scale		x						x						
	13	G-walk Assess (gait cycle duration, step length, propulsion	x						x			x				

		index, support phase percentage D/I, oscillation phase percentage D/I, double support phase percentage, unique support Phase Percentage											
Spasticity	14	NRS		x		x		x		x			
User Satisfaction	15	Gagnon scale		x		x							
Factors epigenetics	16	Homer Gene Based analyses			x					x			x

IC, Informed consent; Patient-Reported Outcome Measures (PROMs), Clinic report, CRO;

Table 1 Assessments

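### The window for recording serious events is undefined and no visit collects adverse events or falls, so injuries between sessions or after training have no planned route of capture and harms cannot be compared between arms

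*Combined protocol and SAP*

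**What the plan says.** Section 3.4 states: "A record of any unexpected Serious Adverse Events (SAE) within trial episodes will be kept". It continues: "These are defined as death, a life-threatening adverse event or an event occurring as a result of the use of the device", the last of these limited to events needing medical intervention. It gives no start or end date for recording.

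The same section provides some tolerability checks. Blood pressure and heart rate are taken weekly. On pain it says: "We will also monitor the appearance of pain in any part of the body related to the RAGT at end of each training session", with type, location and intensity noted. Spasticity is scored on a 0 to 10 scale before each RAGT session.

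Table 1 marks the row "Pain registry" at T1, at the sessions, at T2 and at the visit headed "Follow up at 2 months (T3"), but not at T4.

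The plan itself names relevant hazards. The background lists "fatigue, high risk of falls or high disability" among the factors that limit participation in therapy. The exclusion criteria in section 3.2.2 include "Contraindications for Atalante training (eg, bone instability, history of osteoporosis or osteoporotic fractures") and, among severe concurrent diseases, "infections, circulatory, heart or lung, pressure sores".

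**The concern.** A fall at home, a fracture diagnosed some days after a session or a skin lesion noticed under a strap in the evening need not show during the training hour. Capturing such events needs a stated reporting period and someone asking what has happened since the last contact. The plan has neither. The one record it requires is tied to an undefined term that can be read as the sessions alone, and the visit schedule contains no event question.

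What is at stake is how the safety results can be read. If the trial reports few or no injuries, a reader could not tell whether few occurred or few were asked about. Nor could the two arms be set side by side.

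**Working it through.** The plan states no figure on this point, so the check is mainly a comparison of the text with the schedule.

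**1. The window.** 'Trial episodes' appears once, in section 3.4, and is defined nowhere. The two readings give:

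| Event | Episodes = sessions | Episodes = whole participation |
|---|---|---|
| Serious event as defined, during a session | recorded if unexpected | recorded if unexpected |
| Serious event as defined, between sessions or after training | outside the window, or arguable if caused in a session | recorded if unexpected |
| Home fall, not fatal or life-threatening, not caused by the device | not recorded | not recorded |
| Non-serious injury | not recorded as an event | not recorded as an event |

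The first two rows concern serious events as defined, and there the readings part only on the second. The last two rows come out the same on both.

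**2. The schedule.** The 16 rows of Table 1 are: pain registry, heart rate, arterial pressure, Borg exertion, MFIS, HADS, MSQoL-54, modified Rivermead, EDSS, Berg with Timed Up and Go, 10-metre walk, MSWS-12, G-walk, spasticity NRS, Gagnon satisfaction scale and epigenetics. Rows for adverse events, falls or skin injury: 0 of 16. Section 4 describes no safety analysis.

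**3. What T2 and T3 do offer.** The pain registry is marked at both. The spasticity row has four marks, which read as T1, sessions, T2 and T3, although that row is partly broken in the text available. A painful injury could therefore surface at T2 or T3 as a pain entry. The entry would hold type, location and intensity, but not a fall, event date, seriousness, outcome or relation to training.

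**4. Symmetry between arms.** Section 3.4 words the session pain check around RAGT-related pain and the spasticity check around RAGT sessions. Table 1 heads its session column for robotic sessions. The weekly blood pressure and heart rate check is not restricted to one arm in the text. The third limb of the serious-event definition depends on use of the device, so the cRHB arm cannot meet it.

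**5. Participants who leave.** Section 3.4.2 drops anyone who misses three consecutive sessions, which at three sessions a week is one week. No event question at that moment, and no later assessment, is described. A participant kept away by an injury could leave under that rule without the injury being recorded.

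**6. Illustration with assumed values.** The documents give neither an event risk p nor a share c of events captured. With n = 30 in the RAGT arm (section 3.1), the chance of recording at least one affected participant is 1 − (1 − p·c)^30.

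| Assumed true risk p | c = 1 | c = 0.5 | c = 0.25 |
|---|---|---|---|
| 2% | 45.5% | 26.0% | 14.0% |
| 5% | 78.5% | 53.2% | 31.4% |
| 10% | 95.8% | 78.5% | 53.2% |

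For example, p = 5% and c = 0.5 give 1 − 0.975^30 = 53.2%. The table shows how incomplete capture weakens a report of no events. It does not estimate what this trial would lose.

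**The case against.** The best defence is that 'trial episodes' may simply mean participation in the trial. The definition that follows points that way: death and life-threatening events carry no link to a session, and the device limb is about cause, not the hour of occurrence. A device-caused fracture found days later and needing medical intervention would satisfy it. On that reading no serious event is lost through the window. This stands, and it limits the finding on serious events to an undefined window.

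Second, T2 and T3 are not empty of safety information. Besides pain and apparently spasticity, the mobility, disability, balance and walking tests are repeated there, so a disabling injury could show. This also stands in part, but a worse score or a pain entry does not identify an event, its date or its cause.

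Third, participants are seen three times a week for 8 weeks, and the exclusion criteria lower the risk of bone and skin injury in those enrolled. Both are true. Frequent contact makes an enquiry easy, but the plan does not schedule one.

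A reader might infer more: that injuries outside the sessions are missed, with the loss sized as session hours over calendar hours. The documents do not support this. It takes the narrow reading as fact and overlooks the T2 and T3 measures. It also treats a share of time as a share of events, although device injuries need not spread evenly over the calendar. A reader might also call falls a main safety contrast of the trial. Section 2 states no safety or falls aim, and the background mentions falls only as a limit on participation in therapy.

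**Conclusion.** The concern holds in a limited form. The serious-event window is undefined and may be read as sessions only, and no adverse-event or falls collection is scheduled at any visit. Beyond the pain registry and the apparent spasticity score at T2 and T3, no route is planned for capturing injuries between sessions or after training.

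The part that depends on no reading of 'episodes' is this: falls and injuries outside the serious-event definition are not recorded as events in either arm, and the session-level symptom checks are worded for one arm only. A comparison of harms between RAGT and cRHB cannot be built from such data.

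The size in lost events is unknown, because the documents give no event rate and no capture share. The primary walking-speed comparison is not affected. The point rests on the text and Table 1 as available, with the spasticity row partly broken. It should be corrected because following the plan as written leaves these harms uncollected, and the remedy uses contacts that already exist.

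**What to change.** 1. In section 3.4, replace 'within trial episodes' with: 'from randomisation to the last scheduled follow-up visit, in both arms, whether or not the event occurs during a session'. Name that visit, since Table 1 places T4 at one year while sections 3.1 and 3.4 mention a blood sample, if possible, one year after T4.
2. Add one row to Table 1: 'adverse events since last contact, including falls and skin or bone injury'. Ask it in the same words in RAGT and cRHB at existing session contacts (for example weekly, with the blood pressure and heart rate check), at T2, at each follow-up visit, and when a participant is dropped under section 3.4.2.
3. Record date, seriousness, outcome and relation to training, and report counts by arm in section 4. Base the comparison between arms on this row, because the device limb of the serious-event definition cannot apply to cRHB.

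The cost is modest extra data entry and a longer event listing. Asked weekly, the question comes to at most 60 × 8 = 480 enquiries during training, against 60 × 24 = 1,440 if asked at every session; further detail is needed only for positive answers. No additional visit is required and no clinical rule changes.
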